17.5.1. ECG SPECIFIC DERIVATIONS

QTcF values will be derived from the QT and RR intervals based on the formula of

$$QTcF = \frac{QT}{\sqrt[3]{RR}}$$

If QT and/or RR is missing, the QTcF will be left as missing.

17.5.2. MARKEDLY ABNORMAL CRITERIA

Markedly abnormal criteria for ECG are listed in table below:

Parameter (unit)	Criterion value
Heart Rate (bpm)	>120
	<50
PR Interval (msec)	≥ 210
RR Interval (msec)	> 1200
	< 500
QRS Interval (msec)	≥ 120
	≤ 50
QT Interval (msec)	≥ 500
	≤ 300
QTcF (msec)	> 450

Document: [REDACTED]

Author: [REDACTED]

Version Number: 2.5

Version Date: 18Feb2022

Template No.: [REDACTED]

Reference: CS_WI_BS005

Effective Date: 02Dec2019

	> 480
	> 500
	≤ 300
	Increase from baseline > 30
	Increase from baseline > 60
	Decrease from baseline > 30
	Decrease from baseline > 60
	> 450 and increase from baseline > 30
	> 500 and increase from baseline > 60

17.6. VITAL SIGNS

The following Vital Signs measurements performed within 37 days after the date of last dose of study medication will be reported for this study:

- Heart rate (bpm)
- Respiratory rate (bpm)
- Body Temperature (C)
- Weight (kg)
- Systolic blood pressure (mmHg)
- Diastolic blood pressure (mmHg)

The following summaries will be provided for vital signs data:

- Observed and change from baseline by visit
- The frequency and percentage of patients with any potentially clinically significant findings defined in section 17.6.2 during the treatment period will be presented.

Listing of vital sign data will also be generated.

17.6.1. VITAL SIGNS SPECIFIC DERIVATIONS

There will be no specific derivations for vital signs.

17.6.2. VITAL SIGNS MARKEDLY ABNORMAL CRITERIA

Markedly abnormal quantitative Vital Signs measurements will be identified and classified in accordance with the following predefined criteria:

Vital Sign Parameter	Criterion value
SBP (mmHg), DBP (mmHg), Heart rate (bpm)	Increase from baseline of > 0 - ≤ 20 > 20 - ≤ 40 > 40

Document: [REDACTED]

Author: [REDACTED]

Version Number: 2.5

Version Date: 18Feb2022

Template No.: [REDACTED]

Reference: CS_WI_BS005

Effective Date: 02Dec2019

Vital Sign Parameter	Criterion value
	Decrease from baseline of > 0 - ≤ 20 > 20 - ≤ 40 > 40
Weight (kg)	Percentage decrease from baseline of < 5% ≥ 5 - < 10% ≥ 10 - < 20% ≥ 20% Percentage increase from baseline of < 5% ≥ 5 - < 10% ≥ 10 - < 20% ≥ 20%

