**Table 11 Dose Modification for Hypertension**

AE Grading and Definitions	Dose adjustment	Treatment Suggestions
Grade 1: prehypertension  (systolic BP 120-139 mmHg or diastolic BP 80-89 mmHg)	None	Follow up as planned schedule
Grade 2: SBP 140-159 mmHg or DBP of 90-99 mmHg; or DBP symptomatic increase >20 mmHg	None	Treatment objective: lower the blood pressure to <140/90 mmHg (or <130/80 mmHg in patients with chronic renal disease and/or diabetes).  Refer to Appendix I .
Grade 3: SBP $\geq$ 160 mmHg or DBP $\geq$ 100mmHg; or more than one drug or more intensive therapy are used	Interrupted once Grade3 hypertension lasting more than 7 days after using or adjusting antihypertensive drug; Should the BP of the patient recover to Grade 1 or the baseline level, one time of dose reduction shall be made.	Treatment objective: lower the blood pressure to <140/90 mmHg (or <130/80 mmHg in patients with chronic renal disease and/or diabetes).  Refer to Appendix I .
Grade 4: Life threatening (eg, malignant hypertension, temporary or permanent neurological deficits and hypertensive crisis)	The drug should be terminated.	Emergent medical treatment.

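### SAP 17.6.2 labels every non-zero change in blood pressure, heart rate or weight as markedly abnormal and has no absolute blood-pressure category, so no planned table counts patients by worst measured blood pressure

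*SAP*

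**What the plan says.** SAP Section 17.6.2 introduces its table with "Markedly abnormal quantitative Vital Signs measurements will be identified and classified in accordance with the following predefined criteria". For SBP, DBP and heart rate the lowest band is "Increase from baseline of > 0 - ≤ 20"; in full, the bands are "Increase from baseline of > 0 - ≤ 20 > 20 - ≤ 40 > 40" and "Decrease from baseline of > 0 - ≤ 20 > 20 - ≤ 40 > 40". For weight, both directions start with an open lowest band, for example "Percentage decrease from baseline of < 5" percent, followed by bands from 5%, 10% and 20%. The table contains no absolute SBP or DBP value.

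SAP Section 17.6 then uses this table for a patient count: "The frequency and percentage of patients with any potentially clinically significant findings defined in section 17.6.2 during the treatment period will be presented". The same section plans observed values and changes by visit, and a listing.

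Protocol Table 11 grades hypertension mainly on absolute levels. Grade 2 is "SBP 140-159 mmHg or DBP of 90-99 mmHg" or a symptomatic DBP rise. Grade 3 starts at SBP 160 or DBP 100 mmHg, or is met by intensified drug treatment. Protocol exclusion criterion 8 keeps out patients at or above 140 mmHg systolic or 90 mmHg diastolic.

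**The concern.** A label of markedly abnormal, or potentially clinically significant, should separate patients who matter for safety from ordinary fluctuation. Here a 1 mmHg or 0.1 kg change carries the label. Change bands without an absolute level also cannot be mapped back to the blood-pressure levels that the protocol itself uses.

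This matters because hypertension is a known risk of the drug: Protocol Table 3 prints a frequency of 55.4%. A count by measured value would be a check on blood pressure that does not depend on whether an investigator recorded an adverse event. The SAP has such measured-value summaries for other data: absolute ECG limits in Section 17.5.2 and programmed CTCAE grading of laboratory values in Section 17.4.2. Blood pressure has no equivalent.

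**Working it through.** The plan states no figure for this table, so there is none to reproduce. There are three checks.

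**1. Share of patients counted if the bands are pooled**

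Inputs: Protocol Appendix A schedules vital signs at C1D8, C1D15, C1D22, C2D1, C2D15, C3D1, C3D15 and C4D1, which is k = 8 post-baseline visits through C4D1 (Day 1 serves as baseline). The documents give no variability, so the following are assumptions.

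- *Exchangeable readings, no drug effect, no ties.* The baseline is the highest of k + 1 readings with probability 1/(k + 1). So P(at least one rise) = 1 − 1/(k + 1) = k/(k + 1). For k = 8 this is 8/9 = 89%; for k = 5, 5/6 = 83%; for k = 11, 11/12 = 92%. By symmetry the same share has at least one fall. Without ties, every patient has one or the other.
- *Allowing ties.* Take the change as Normal(0, SD), rounded to whole mmHg, with SD assumed between 5 and 15 mmHg. For one parameter at one visit, P(non-zero) = 1 − [Φ(0.5/SD) − Φ(−0.5/SD)] = 92.0% (SD 5), 96.0% (SD 10) or 97.3% (SD 15). Treating visits as independent, two visits give 99.4%, 99.8% and 99.9%, and seven give 100% to the precision computed. Visits share a baseline, so independence overstates the multi-visit figures. The single-visit 92% to 97% is a floor under this model.

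**2. What the upper bands show if kept separate**

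Under the same noise-only model with seven independent visits, a rise above 20 mmHg occurs at least once in 0.01% (SD 5), 3.6% (SD 8), 13% (SD 10), 27% (SD 12) or 47% (SD 15) of patients. A rise above 40 mmHg occurs in 0% to 2.4%. These bands discriminate; the lowest does not.

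**3. Change bands against the Table 11 measured levels**

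| Baseline to reading (mmHg) | Change | SAP 17.6.2 band | Table 11 level |
|---|---|---|---|
| DBP 80 to 81 | +1 | lowest | Grade 1 |
| DBP 80 to 100 | +20 | lowest | Grade 3 |
| SBP 120 to 140 | +20 | lowest | Grade 2 |
| SBP 100 to 121 | +21 | middle | Grade 1 |
| SBP 139 to 160 | +21 | middle | Grade 3 |

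Any baseline DBP of 80 to 89 can reach 100 to 109 within the lowest band. For SBP the lowest band can hide 140 to 159 but not 160 or more: from a baseline below 140 the smallest rise needed is 160 − 139 = 21. This assumes that the analysis baseline respects the entry limits.

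**The case against.** **The bands may never be pooled.** Section 17.6.2 says that measurements are classified, the cut-points would serve no purpose in a single yes/no count, and the ECG criteria are tiered in the same way. The table shells are not in the documents. This stands: the near-100% figure applies only to a pooled count, which the wording of Section 17.6 allows but does not compel. It does not answer check 3, which holds with the bands separate.

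**A reader might infer that hypertension cannot be seen, or that investigator-reported events are the only evidence left.** The documents do not support that.
- SAP Section 17.2.6 makes hypertension an adverse event of special interest, summarised by preferred term, severity and relationship, with time to first event.
- Section 17.6 summarises SBP and DBP by visit, and Section 7 specifies quartiles, minimum and maximum for continuous variables. Individual values are listed.

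What these do not give is a patient count. By-visit summaries leave out unscheduled readings (Section 5.3), and where several readings fall in a window the one nearest the scheduled day is used (Section 5.4), so a peak can be missed.

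**Adverse event reporting is not purely discretionary.** Protocol Section 7.1.8.4 requires an event when an abnormal vital sign leads to intervention or to a change in study or concomitant treatment, and Table 11 gives a treatment objective from Grade 2. This largely stands. An untreated, symptom-free reading that the investigator does not consider important could still go unreported.

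**A reader might also rank hypertension as the most frequent identified risk.** Its 55.4% is the highest percentage printed in Protocol Table 3, but palmar-plantar erythrodysesthesia, rash and dermatitis have no percentage there, so the ranking cannot be confirmed.

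**Measured limits do not reproduce the Table 11 grades,** because Grade 2 can rest on symptoms and Grade 3 on drug treatment. This stands and governs how the added rows are labelled.

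**Conclusion.** The labelling defect is certain from the text: the lowest bands bring every non-zero change under the heading of markedly abnormal. The absence of an absolute SBP or DBP category is equally plain, and no planned table counts patients by worst measured blood pressure.

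The size depends on the layout. Pooled, the count takes in essentially every patient and says nothing about the drug; the 89% with at least one rise rests on exchangeable, tie-free readings at 8 visits. Separate, the upper bands are useful but cannot identify who reached a Table 11 level.

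Severity is minor. This is a descriptive safety table in a study without hypothesis tests (SAP Section 5.5). The primary endpoint is unaffected, and hypertension is still reported elsewhere.

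**What to change.** In SAP Sections 17.6 and 17.6.2:

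1. Remove the bands of more than 0 to 20 (SBP, DBP, heart rate) and under 5% (weight) from the markedly abnormal or potentially clinically significant count. Keep them, if wanted, as descriptive change categories.
2. Show the remaining bands as separate rows, by direction, and state that they are not pooled.
3. Add the number and percentage of patients whose worst post-baseline value, including unscheduled readings, is SBP ≥140 and ≥160 mmHg, or DBP ≥90 and ≥100 mmHg. Label these as measured levels taken from Protocol Table 11, not as hypertension grades.

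The new rows are reporting categories only and change no clinical rule. The cost is SAP wording and one table shell; the readings are already collected.

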17.7. PHYSICAL EXAMINATION

The physical examination results collected will be listed.

17.8. OTHER SAFETY ASSESSMENTS

17.8.1. ECOG PERFORMANCE STATUS

Summary of ECOG performance status by scheduled visit and change to worst post-baseline value will also be presented. All the ECOG performance status data will also be listed.

17.8.2. ECHOCARDIOGRAM

Baseline and change from baseline on left ventricular ejection fraction (LVEF) will be summarized by dose cohort (only in dose escalation phase) or tumor specific cohorts (only in dose expansion phase) and visit. Also, shift from baseline to worst post-baseline overall evaluation (i.e., normal, abnormal but NCS, abnormal and CS) will be summarized. Individual data will also be listed.

17.8.3. PREGNANCY TEST

Individual pregnancy information will be listed for the SAS.

17.8.4. TUMOR MARKER

CA125 level for patients with ovarian cancer, PSA for patients with prostate cancer, or other tumor markers (as appropriate) should be obtained as clinically indicated or with each tumor assessment. The individual tumor marker test results will be listed for SAS.

Document:

Author:

Version Number:

2.5

Version Date:

18Feb2022

Template No.:

Reference: CS_WI_BS005

Effective Date: 02Dec2019

17.8.5. IMPACT OF COVID-19

The study is conducted during the COVID-19 pandemic, additional data is collected for evaluating the impact of COVID-19. To eliminate potential hazards to patients and study staff due to the COVID-19 pandemic while ensuring patients safety and maintaining data integrity, patients are allowed remote visits during the pandemic. Data listing will be provided.

APPENDIX 1. SCHEDULE OF EVENTS

Schedule of events is shown as below.

Appendix A Study Schedule of Events

Procedure	Date	Treatment ²								Treatment Completion ³	Follow-up	
		Screening		Cycle 1				Cycle 2-3				Cycle 4 and onwards
		Day -28 to Day -1	Day -7 to Day -1	Day 1	Day 8 (±1d)	Day 15 (±1d)	Day 22 (±1d)	Day 1 (±3d)	Day 15 (±3d)			Day 1 of each subsequent cycle (±3d)
Informed consent ¹	X											
Tumor assessment (Dose Escalation, Expansion Cohorts C, D, E)	X		Screening, then every 8 (±1) weeks thereafter (eg C3D1, C5D1, C7D1, etc.)								X ⁴	
Tumor assessment (Dose Expansion Cohorts A and B only)	X		Screening, C2D1, C3D1 C4D1, and every 8 (±1) weeks thereafter (eg C6D1, C8D1, C10D1, etc.)								X ⁴	
Medical history, demographics	X											
Concomitant medication ⁵	X	X	X	X	X	X	X	X	X	X		
ECOG performance status		X	X		X		X	X	X	X		
Vital signs ⁶		X	X	X	X	X	X	X	X	X		
Complete physical examination ⁷		X										
Limited physical examination ⁷			X	X	X	X	X	X	X	X		
Height	X											
Hematology ⁸		X	X	X	X	X	X	X	X	X		
Coagulation assay (aPTT, INR)		X	X	X	X	X	X	X	X	X		
Chemistry panel ⁹		X	X	X	X	X	X	X	X	X		
Urinalysis ¹⁰		X	X	X	X	X	X	X	X	X		
Echocardiogram ¹¹	X		X (Every 12 weeks ± 1 week after the first dose)								X	
Thyroid function test ¹²	X						X		X	X		
Serum pregnancy tests ¹³		X								X		
Urine pregnancy tests ¹³							X		X			
Specific tumor markers ¹⁴ Dose Escalation, Expansion Cohorts C, D, E)	X		Screening, then every 8 (±1) weeks thereafter: C3D1, C5D1, C7D1, etc									
Specific tumor markers ¹⁴ Dose Expansion Cohorts A and B only)			Screening, C2D1, C3D1 C4D1, and every 8 (±1) weeks thereafter									
12-lead electrocardiogram ¹⁵		X	X		X		X		X	X		
PK plasma sampling			PK samples are being collected on Days 1, 2, 14, and 15 of Cycle 1 for Expansion Cohorts B, C, D, and E. Refer to Appendix D for									
			specific timepoints									
Adverse event ¹⁶	X	X	X	X	X	X	X	X	X	X		
Fruquintinib treatment			Once daily, 3 weeks on/ 1 week off									
Survival follow up ¹⁷											X	

Document: [REDACTED]

Author: [REDACTED] Version Number: 2.5
 Version Date: 18Feb2022

Template No.: [REDACTED] Reference: CS_WI_BS005

Effective Date: 02Dec2019

Note:

1. A written informed consent form should be obtained prior to any protocol-specific procedure or test. Tests completed within 28 days prior to enrollment can be used for screening and do not need to be repeated (except hematology, coagulation test, clinical chemistry, or urinalysis results).
2. Unless otherwise indicated, the visit window during the treatment period will be ± 3 days (± 1 day during cycle 1).
3. Patients who complete or prematurely discontinue the study need to return to the study site for a follow-up at 30 (± 7) days after the decision to discontinue treatment permanently. Ongoing AEs will be followed until the event has resolved to baseline grade, the event is assessed as stable by the investigator, new anti-tumor treatment is initiated, the patient is lost to follow-up, the patient withdraws consent, or when it has been determined that the study treatment or participation is not the cause of the AE.
4. The treatment completion visit tumor assessment can be omitted if treatment ended because of disease progression or the patient had a tumor assessment within 14 days prior to the last dose of study drug.
5. Concomitant medication includes any prescribed or over-the-counter medicines. All medication used by patients within 7 days before screening and 30 days after study treatment completion should be recorded. At each visit, all medication used since the prior visit should be recorded.
6. Vital signs include blood pressure, heart rate, respiratory rate, and temperature. For patient with a baseline history of antihypertensive medications, blood pressure should be monitored at 3 hours (± 2 hours) after the daily doses of anti-hypertensive medication.
7. Please refer to Section 6.3.2 for the assessments that should be completed as part of the Complete and Limited Physical Exams.
8. Hematology consists of complete blood count, including red blood cell count, hemoglobin, hematocrit, reticulocyte count, white blood cell count with differential (neutrophils, bands, lymphocytes, eosinophils, monocytes, basophils, and other cells), and platelet count.
9. The chemistry panel includes blood urea nitrogen, creatinine and creatinine clearance, sodium, potassium, chlorine, bicarbonate, calcium, magnesium, phosphorus, glucose, alanine aminotransferase, bilirubin (total), aspartate aminotransferase, alkaline phosphatase, lactate dehydrogenase, total cholesterol, triglycerides, uric acid, protein (total) and albumin.
10. Urinalysis includes pH, glucose, protein, and blood. A 24-hour urine should be collected from all patients with $>1+$ proteinuria for quantitative test of urine protein during the screening. If protein $\geq 2+$ during the period of study treatment, a 24-hour urine test should be conducted within 1 week.
11. MUGAs are permitted if echocardiograms cannot be performed.
12. Includes free T3, free T4, and thyroid-stimulating hormone (TSH).
13. Women of childbearing potential will receive a serum pregnancy test during screening and within 30 days after treatment completion, and a urine pregnancy test on Day 1 of each 28-day cycle beginning at Cycle 2. If pregnancy is suspected, additional tests should be completed. In the case of menopausal women, the date of menopause onset should be recorded.
14. CA125 level for patients with ovarian cancer, PSA for patients with prostate cancer, or other tumor markers (as appropriate) should be obtained as clinically indicated or with each tumor assessment.
15. On Days 1 and 15 in Cycle 1, ECG should be performed at pre-dose and at 3 hours (± 15 minutes) post-dose (around C_{max} after single dose and at steady state in order to evaluate concentration-QT relationship for fruquintinib). Untimed ECG will be conducted on Day 1 of each cycle from Cycle 2 and onward.
16. After informed consent, all SAEs and concomitant medications will be collected. After initiation of study drug, all AEs and SAEs will be collected until 30 days following the last dose of study drug or a new treatment of anti-tumor therapy, whichever is earlier. After this period, investigators should report only SAEs that are considered to be related to the study drug.
17. **For subjects in Expansion Cohorts B, C, D, and E** - Survival follow-up (by telephone) should be performed every 12 (± 2) weeks from the date of the Treatment Completion visit. All subsequent anti-tumor therapy and information about ongoing or unresolved study drug-related SAEs will be collected. For the patients that discontinue the study without PD, all available tumor assessment results during survival follow-up will be recorded in the CRF until confirmation of PD. The date and cause of death should be recorded, if applicable. Patients who withdraw consent are encouraged to be followed for survival. If the patient has clearly expressed his/her refusal to be followed after withdrawal of consent, he/she will terminate the study and no survival follow-up will be performed.

Document:

Author:

Version Number:

2.5

Version Date:

18Feb2022

Template No.:

Reference: CS_WI_BS005

Effective Date: 02Dec2019

APPENDIX 2. PROGRAMMING CONVENTIONS FOR OUTPUTS

Output Conventions

For more details please refer to the general rules listed in the shell.

Dates & Times

Depending on data available, dates and times will take the form ddmmyyyyThh:mm:ss.

Spelling Format

English US.

Presentation of Treatment Groups

For outputs, treatment groups will be represented as follows and in that order:

Treatment Group	For Tables
Dose Escalation Phase: 3mg QD	Dose Escalation Phase: Fruquintinib 3mg QD
Dose Escalation Phase: 5mg QD	Dose Escalation Phase: Fruquintinib 5mg QD
Dose Expansion Phase (5mg QD): Cohort A	Dose Expansion Phase: Cohort A
Dose Escalation Phase: 5mg QD + Dose Expansion Phase (5mg QD): Cohort A	Dose Expansion Phase: Dose Escalation Fruquintinib 5mg QD + Cohort A
Dose Escalation Phase + Dose Expansion Phase	Dose Expansion Phase: Dose Escalation Phase + Dose Expansion Phase (Only for Patient Disposition, Demographic and Baseline Characteristics, Baseline Cancer Characteristics tables)

Treatment Group	For Listings
Dose Escalation Phase: 3mg QD	Dose Escalation Phase: Fruquintinib 3mg QD
Dose Escalation Phase: 5mg QD	Dose Escalation Phase: Fruquintinib 5mg QD
Dose Expansion Phase (5mg QD): Cohort A	Dose Expansion Phase: Cohort A

Treatment Group	For Figures
Dose Escalation Phase: 3mg QD	Dose Escalation Phase: Fruquintinib 3mg QD
Dose Escalation Phase: 5mg QD	Dose Escalation Phase: Fruquintinib 5mg QD

Document: [REDACTED]

Author: [REDACTED]

Version Number:

2.5

Version Date:

18Feb2022

Template No.: [REDACTED]

Reference: CS_WI_BS005

Effective Date: 02Dec2019

Treatment Group	For Figures
Dose Expansion Phase (5mg QD): Cohort A	Dose Expansion Phase: Cohort A
Dose Escalation Phase: 5mg QD and Dose Expansion Phase (5mg QD): Cohort A	Pooling Dose Escalation 5 mg and Cohort A
Dose Escalation Phase: 3mg QD + Dose Escalation Phase: 5mg QD and Dose Expansion Phase (5mg QD): Cohort A	Dose Escalation 3mg and Pooling Dose Escalation 5mg and Cohort A

Presentation of Visits

For outputs, visits will be represented as follows and in that order:

Long Name (default)	Short Name
Baseline	Baseline
Cycle 1 Day 1	C1D1
Cycle 1 Day 8	C1D8
Cycle 1 Day 15	C1D15
Cycle 1 Day 22	C1D22
Cycle 2 Day 1	C2D1
Cycle 2 Day 15	C2D15
Cycle 3 Day 1	C3D15
Cycle 4 Day 1	C4D1
Cycle X Day 1	CXD1
.....
End of Treatment	EOT

Listings

All listings will be ordered by the following (unless otherwise indicated in the template):

Assigned treatment group, unless otherwise specified

Center-Patient Number

Date (where applicable)

Document: [REDACTED]

Author: [REDACTED]

Version Number:

2.5

Version Date:

18Feb2022

Template No.: [REDACTED]

Reference: CS_WI_BS005

Effective Date: 02Dec2019

APPENDIX 3. BEST OVERALL RESPONSE WHEN CONFIRMATION OF CR AND PR ARE REQUIRED

First TPR	Second TPR[a]	Best overall response*^ for ORR	Best Overall Response for ORR _{UNCONFIRMED}
CR	CR	CR	CR
CR	PR	SD [b] or PD	Unconfirmed CR
CR	SD	SD [b] or PD	Unconfirmed CR
CR	PD	SD [b] or PD	Unconfirmed CR
CR	NE or NA	SD [c] or NE or NA	Unconfirmed CR
PR	CR	PR	Unconfirmed CR
PR	PR	PR	PR
PR	SD	SD [d]	Unconfirmed PR
PR	PD	SD [b] or PD	Unconfirmed PR
PR	NE or NA	SD [c] or NE or NA	Unconfirmed PR
NE	NE	NE	NE
NE	CR	SD	Unconfirmed CR
NE	PR	SD	Unconfirmed PR
NE	SD	SD	SD
NE or NA	PD	PD	PD
SD	PD	SD [b] or PD	SD [b] or PD
SD	CR	SD	SD
SD	PR	SD	SD
SD	SD	SD	SD
SD	NE or NA	SD [c] or NE or NA	SD [c] or NE
PD	No further evaluation	PD	PD

CR = Complete Response; NE = Not Evaluable; NA = Not Available; ORR = Objective Response Rate; PD = Progressive Disease; PR= Partial Response; SD = Stable Disease.

[a]The minimum interval for confirmation of CR and PR is 4 weeks.

[b]Best response will be SD if the first time point overall response is after 49 days on study. Otherwise, the best response will be PD.

[c]Best response will be SD if the first time point overall response after 49 days on study. Otherwise, the best response will be NE.

Document: [REDACTED]

Author: [REDACTED]

Version Number: 2.5

Version Date: 18Feb2022

Template No.: [REDACTED]

Reference: CS_WI_BS005

Effective Date: 02Dec2019

[d]Best response will be SD provided the criteria for PD have not been met from the first to second assessment.

* A best overall response of SD can only be made after the subject is on study for a minimum of 49 days (counted from Cycle 1 Day 1). If the subject is on study for less than 49 days, any tumor assessment indicating stable disease before this time period will have a best response of NE unless PD is identified.

^ Subsequent documentation of a CR may provide confirmation of a previously identified CR even with an intervening NE (e.g., CR NE CR). Subsequent documentation of a PR may provide confirmation of a previously identified PR even with an intervening NE or SD (e.g., PR NE PR or PR SD PR). However, only one (1) intervening NE or SD will be allowed between PRs for confirmation. Note: in the following scenario, PR SD NE PR, the second PR is not a confirmation of the first PR.

Document: [REDACTED]

Author: [REDACTED]

Version Number:

2.5

Version Date:

18Feb2022

Template No.: [REDACTED]

Reference: CS_WI_BS005

Effective Date: 02Dec2019

